8.1 ASSESSING AND RECORDING ADVERSE EVENTS

An adverse event is defined as any untoward medical occurrence in a patient or clinical investigation subject administered a pharmaceutical product and which does not necessarily have to have a causal relationship with this treatment. An adverse event can therefore be any unfavorable and unintended sign (including an abnormal laboratory finding, for example), symptom, or disease temporally associated with the use of a medicinal product or protocol-specified procedure, whether or not considered related to the medicinal product or protocol-specified procedure. Any worsening (i.e., any clinically significant adverse change in frequency and/or intensity) of a preexisting condition that is temporally associated with the use of the Merck's product, is also an adverse event.

Changes resulting from normal growth and development that do not vary significantly in frequency or severity from expected levels are not to be considered adverse events. Examples of this may include, but are not limited to, teething, typical crying in infants and children and onset of menses or menopause occurring at a physiologically appropriate time.

Merck product includes any pharmaceutical product, biological product, device, diagnostic agent or protocol-specified procedure, whether investigational (including placebo or active

comparator medication) or marketed, manufactured by, licensed by, provided by or distributed by Merck for human use.

Adverse events may occur during the course of the use of Merck product in clinical trials, or as prescribed in clinical practice, from overdose (whether accidental or intentional), from abuse and from withdrawal.

All adverse events that occur after the consent form is signed but before treatment allocation/randomization must be reported by the investigator if they cause the subject to be excluded from the trial, or are the result of a protocol-specified intervention, including but not limited to washout or discontinuation of usual therapy, diet, placebo treatment or a procedure.

The investigator is responsible for ensuring that all AEs and SAEs that are observed or informed by the patient during the study are collected and reported, and to assign appropriate attribution to the study treatment.

From the time of initiation of pembrolizumab through 30 days after surgery, all adverse events must be reported by the investigator. Additionally, all adverse events meeting serious criteria, from time of treatment initiation through 90 days following cessation of study treatment, or 30 days following cessation of study treatment if the participant initiates new anti cancer therapy should be reported by the investigator. All adverse events will be logged into a protocol-specific REDCap database. The reporting timeframe for adverse events meeting any serious criteria is described in section 8.3.1. The investigator will make every attempt to follow all subjects with related non-serious adverse events for outcome or until resolution to grade 0-1.

8.2 Definition of an Overdose for This Protocol and Reporting of Overdose to the Sponsor and to Merck

For purposes of this trial, an overdose of pembrolizumab will be defined as any dose of 1,000 mg or greater (≥ 5 times the indicated dose). No specific information is available on the treatment of overdose of pembrolizumab. Appropriate supportive treatment should be provided if clinically indicated. In the event of overdose, the subject should be observed closely for signs of toxicity. Appropriate supportive treatment should be provided if clinically indicated.

If an adverse event(s) is associated with (“results from”) the overdose of a Merck product, the adverse event(s) is reported as a serious adverse event, even if no other seriousness criteria are met.

If a dose of Merck’s product meeting the protocol definition of overdose is taken without any associated clinical symptoms or abnormal laboratory results, the overdose is reported as a non-serious Event of Clinical Interest (ECI), using the terminology “accidental or intentional overdose without adverse effect.”

All reports of overdose with and without an adverse event must be reported within 5 working days to MDACC's IND Office and within 2 working days to Merck Global Safety. (Attn: Worldwide Product Safety; [contact])

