5.2.1 Dose Selection

The rationale for selection of doses to be used in this trial is provided in Section 4.2.2.

Details on preparation and administration of pembrolizumab are provided in the Pharmacy Manual.

5.2.2 Dose Modification and toxicity management for immune-related AEs associated with pembrolizumab

AEs associated with pembrolizumab exposure may represent an immunologic etiology. These immune-related AEs (irAEs) may occur shortly after the first dose or several months after the last dose of pembrolizumab treatment and may affect more than one body system simultaneously. Therefore, early recognition and initiation of treatment is critical to reduce complications. Based on existing clinical study data, most irAEs were reversible and could be managed with interruptions of pembrolizumab, administration of corticosteroids and/or other supportive care. For suspected irAEs, ensure adequate evaluation to confirm etiology or exclude other causes. Additional procedures or tests such as bronchoscopy, endoscopy, skin biopsy may be included as part of the evaluation. Based on the severity of irAEs, withhold or permanently discontinue pembrolizumab and administer corticosteroids. Dose modification and toxicity management guidelines for irAEs associated with pembrolizumab are provided in Table 3.

Table 3: Dose modification and toxicity management guidelines for immune-related AEs associated with pembrolizumab

General instructions:

1. Corticosteroid taper should be initiated upon AE improving to Grade 1 or less and continue to taper over at least 4 weeks.
2. For situations where pembrolizumab has been withheld, pembrolizumab can be resumed after AE has been reduced to Grade 1 or 0 and corticosteroid has been tapered. Pembrolizumab should be permanently discontinued if AE does not resolve within 12 weeks of last dose or corticosteroids cannot be reduced to ≤ 10 mg prednisone or equivalent per day within 12 weeks.
3. For severe and life-threatening irAEs, IV corticosteroid should be initiated first followed by oral steroid. Other immunosuppressive treatment should be initiated if irAEs cannot be controlled by corticosteroids.

Immune-related AEs	Toxicity grade or conditions (CTCAEv4.0)	Action taken to pembrolizumab	irAE management with corticosteroid and/or other therapies	Monitor and follow-up

Proprietary Information of MD Anderson

2017-0057

January 9, 2019

Page 17

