6.0 STUDY FLOW CHART

STUDY PHASE	SCREENING PHASE	TREATMENT PHASE				FOLLOW-UP PHASE	EARLY TREATMENT DISCONTINUATION
VISIT/CYCLE	SCREENING	CYCLE #1 (Week 1)	CYCLE #2 (Week 4)	PRE-OP/SAFETY VISIT (Week 7)	SURGERY (Week 6- 8)	FOLLOW-UP	
Scheduling window (days)	-28 to -1	1(± 3)	21(± 3)	35-49(± 3)	42-56(± 3)	30 day (± 7) and 90 day (± 7) Post Op	
Informed Consent	X						
Inclusion/Exclusion Criteria	X						
Demographics/Medical history	X						
Concomitant Medications	X	X	X	X	X	X ⁸	X ⁸
Pembrolizumab Administration		X	X				
Assessment of Disease Extent ¹	X						
Review of Adverse Events	X	X	X	X	X	X	X
Full Physical Exam	X						X
Directed Physical Exam		X	X	X		X	
Vital Signs and Weight	X	X ²	X ²	X		X	X
ECOG Performance Status	X	X	X	X		X	X
Pregnancy Test	X	X ³					
PT/INR and aPTT	X ⁹	X	X	X		X	X
CBC with Diff	X ⁹	X	X	X		X	X

Proprietary Information of MD Anderson

2017-0057

January 9, 2019

Page 28

Comprehensive Metabolic Panel ⁴	X ⁹	X	X	X		X	X
Urinalysis ⁵	X ⁹	X	X	X		X	X
T3, FT4 and TSH	X ⁹	X	X	X		X	X
Pulmonary Function Tests	X						
ACTH, Cortisol	X	X	X				
ESR, CRP	X	X	X				
Testosterone, FSH, LH (males)	X	X	X				
Estrogen, FSH, LH (females)	X	X	X				
Archival Tissue Collection ⁶	X				X		
Feces and Urine for microbiome studies	X			X		X ¹⁰	
Blood for Correlative Studies ⁷	X		X	X		X	
Cystectomy					X		

¹ A complete assessment of disease extent will be made at screening per SOC guidelines, and will include but not be limited to diagnostic endoscopy with biopsy/resection of the index lesion for pathologic diagnosis. Additionally an examination and assessment for palpable disease will be made. Cross sectional imaging of the chest, abdomen and pelvis with the addition of whole body nuclear medicine bone imaging where clinically indicated will complete the staging evaluation. Exams performed within 6 weeks prior to screening will be accepted for inclusion in the study if deemed appropriate by the treating physician

² Pre and post pembrolizumab dose during treatment administration days

³ Female subjects of childbearing potential should have a negative urine or serum pregnancy test within 72 hours prior to receiving the first dose of study medication. If the urine test is positive or cannot be confirmed as negative, a serum pregnancy test will be required.

⁴ Includes: Albumin, alkaline phosphatase, ALT, AST, LDH, electrolytes, uric acid, calcium, glucose, phosphorus, magnesium, total bilirubin, total protein, BUN and creatinine

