7.6 Adverse Event (AE) Monitoring

The investigator or qualified designee will assess each subject to evaluate for potential new or worsening adverse events throughout the duration of the study. Adverse events will be graded according to NCI CTCAE Version 4.0. Toxicities will be characterized in terms regarding seriousness, causality, toxicity grading, and action taken with regard to study treatment. Refer to Section 8 for further details regarding assessing and recording adverse events.

Any related adverse events Grade >1 which are present at the time of discontinuation/withdrawal should be followed until the resolution of the AE to Grade 0-1.

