- Unless otherwise noted, the electronic SAE application (eSAE) will be utilized for safety reporting to the IND Office and MDACC IRB.
- Serious adverse events will be captured from the time of the first protocol-specific intervention, until 90 days after cessation of study treatment, or 30 days following cessation of study treatment if the subject initiates new anticancer therapy, unless the participant withdraws consent. Serious adverse events must be followed until clinical recovery is complete and laboratory tests have returned to baseline, progression of the event has stabilized, or there has been acceptable resolution of the event.
- Additionally, any serious adverse events that occur after the time period noted above that are related to the study treatment must be reported to the IND Office. This may include the development of a secondary malignancy.

Reporting to FDA:

- Serious adverse events will be forwarded to FDA by the IND Sponsor (Safety Project Manager IND Office) according to 21 CFR 312.32.

It is the responsibility of the PI and the research team to ensure serious adverse events are reported according to the Code of Federal Regulations, Good Clinical Practices, the protocol guidelines, the sponsor's guidelines, and Institutional Review Board policy.

SAE reports and any other relevant safety information are to be forwarded to the Merck Global Safety [contact]

A copy of all 15 Day Reports and Annual Progress Reports is submitted as required by FDA, European Union (EU), Pharmaceutical and Medical Devices agency (PMDA) or other local regulators. Investigators will cross reference this submission according to local regulations to the Merck Investigational Compound Number (IND, CSA, etc.) at the time of submission.

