9.4 Analysis Plan

TOX events will be reported with a 95% credible interval assuming a non-informative prior of beta (1,1). Specific events will also be summarized. Then all adverse events and surgical complications will be reported overall by grade, attribution, and treatment period (cycle 1, cycle 2, between the end of cycle 2 and actual surgery, 30 days following surgery). Demographic and baseline laboratory results will be summarized using descriptive and graphical statistics. Changes in markers between biopsy and surgical resection will be compared with a paired t-test or non-parametric alternative as indicated for continuous measures, and with McNemar's test for binary or ordinal measures. The numbers of patients with sufficient samples for laboratory analysis will be used to plan the numbers of patients needed for enough evaluable samples future trials. Similarly this experience will guide planning for the numbers and types of markers that can be reasonably assessed from surgical specimens in this patient population after 'window of opportunity' pembrolizumab treatment.

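### Full adverse event reporting ends 30 days after surgery in Section 8.1, in conflict with sections that follow events to the 90-day visit, so late non-serious toxicity may be under-reported

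*Combined protocol and SAP*

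**What the plan says.** Reporting windows:

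- **All adverse events.** Section 8.1: "From the time of initiation of pembrolizumab through 30 days after surgery, all adverse events must be reported by the investigator".
- **Serious adverse events.** Section 8.1 runs these "from time of treatment initiation through 90 days following cessation of study treatment", and 8.3.1 likewise captures them "until 90 days after cessation of study treatment". Both shorten the window to 30 days if new anticancer therapy begins. Section 8.3.1 adds that serious events "that occur after the time period noted above that are related to the study treatment must be reported to the IND Office", with no end date.
- **Events of clinical interest.** Section 8.3.2 sets 90 days after the last dose, whatever the attribution, with the same shortening. It lists two: an overdose without clinical consequences, and a combined transaminase-bilirubin-alkaline phosphatase criterion.

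Text pointing to a longer period:

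- Section 7.6 has events assessed "throughout the duration of the study".
- Section 7.8 treats clinically significant examination changes, in follow-up as well as treatment, as adverse events to be recorded.
- Section 8.1, before its 30-day sentence, makes the investigator responsible for collecting and reporting every event seen or volunteered while the study runs.
- Section 8.3.4 adopts the phase I recording scheme: all grades, all attributions.
- The flow chart's follow-up column, headed "30 day (± 7) and 90 day (± 7) Post Op", marks adverse event review, blood count, metabolic panel and thyroid tests.

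Section 5.2.2 warns that immune-related events can arise "several months after the last dose of pembrolizumab treatment". Section 9.4 tabulates events overall by grade, attribution and treatment period. The last two of its four periods are "between the end of cycle 2 and actual surgery, 30 days following surgery".

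**The concern.** The primary objective (Section 3.1.1) is to characterise the safety profile, and Section 9.1 says the secondary endpoints will feed the design of later studies. The protocol expects some immune-related toxicity to appear late, and it schedules a visit at which such toxicity could be found. Yet the most explicit reporting sentence stops well before that visit. A new thyroid, skin or bowel event that is not serious, first seen at 90 days, meets one rule that says to collect it and another under which reporting has ended.

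Staff could reasonably follow either. Capture could then differ from patient to patient, and an omission can only lower the reported frequency. In a 20-patient study one patient is 1/20 = 5 percentage points.

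**Working it through.** **Inputs** (flow chart, nominal days): dose 2 on day 21; surgery on day S, from 42 to 56; follow-up visits at S + 30 and S + 90. Reporting windows are as in Sections 8.1, 8.3.1 and 8.3.2.

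**Reproducing the plan's own figures.** Section 9.1.1 calls the TOX interval approximately 3 months: 42 + 14 + 30 = 86 days, or 86/7 = 12.3 weeks. The synopsis gives participation of up to 25 weeks: 28 + 56 + 90 = 174 days, or 174/7 = 24.9 weeks. Both agree, so the calendar is being read as intended.

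**Where each window closes.**

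| Quantity | Formula | S = 42 | S = 56 |
|---|---|---|---|
| Full reporting ends (day) | S + 30 | 72 | 86 |
| Same, days after dose 2 | S + 30 − 21 | 51 | 65 |
| Serious-event and clinical-interest window ends (day) | 21 + 90 | 111 | 111 |
| That window beyond the full-reporting cut-off (days) | 111 − (S + 30) | 39 | 25 |
| 90-day visit (day) | S + 90 | 132 | 146 |
| Full-reporting cut-off to 90-day visit (days) | (S + 90) − (S + 30) | 60 | 60 |
| Serious-event window end to 90-day visit (days) | S + 90 − 111 | 21 | 35 |

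The serious-event window covers 39/60 = 65% to 25/60 = 42% of the interval between the two follow-up visits.

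**Sensitivity to visit windows.** With ±3 days on dose 2 the serious-event window closes on day 108-114. With ±3 days on surgery and ±7 on the visit, the 90-day visit falls between 39 + 90 − 7 = 122 and 59 + 90 + 7 = 156. The shortfall stays positive, from 122 − 114 = 8 to 156 − 108 = 48 days.

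**What is reportable in the last 60 days of follow-up, if the 30-day sentence governs.**

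- Related serious events: yes, with no end date.
- Unrelated serious events: to day 111 only. Section 8.3.1 separately sends serious events arising while the protocol runs to the ethics board under an institutional policy not reproduced here, so the position after day 111 is unclear.
- Events of clinical interest: to day 111.
- All other non-serious events: no. Section 8.1 asks for related non-serious events to be followed to grade 0-1, but that gives no rule for reporting events that begin after the cut-off.

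**How often this might matter.** The documents give no rate for late events, so the rates here are assumptions. If each patient has probability r of a new, unreported late event, the chance of at least one among 20 is 1 − (1 − r)^20: 18% for r = 1%, 33% for 2%, 64% for 5% and 88% for 10%.

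**Effect on the main safety rule.** TOX is defined separately in Section 9.1.1 and ends at the 30-day surgical assessment. A descriptive later period changes neither the stopping boundary nor the credible interval nor the sample size.

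**The case against.** A reader might infer that adverse event reporting as a whole stops 30 days after surgery, so that late toxicity is seen and then discarded. The documents do not support that. Serious events and events of clinical interest continue to 90 days after the last dose, and related serious events continue indefinitely, so late serious drug toxicity is reported.

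Nor is loss of non-serious events established. The broad duty in Section 8.1, the phase I scheme in 8.3.4, and a sentence in 8.1 that logs all adverse events in the study database without a time limit all point to fuller capture. In 9.4 the list of periods does not expressly exclude later events from the overall tables, and Section 2.1.3 holds the primary analysis until follow-up is complete.

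The sponsor could add that the cut-off looks deliberate: concomitant medications follow the same tiers, being recorded beyond 30 days after surgery only for serious events and events of clinical interest (Sections 5.5.1 and 7.5, flow chart footnote 8). No late-event rate is given, and no decision in the trial changes.

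These points stand, and they narrow the finding. They do not remove it. The clinical-interest list is too short to act as a general safety net. The broad duty and the 30-day limit sit in the same section without a rule of precedence. A deliberate cut-off would still conflict with 7.6, 7.8 and 8.3.4.

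**Conclusion.** The plan contradicts itself on how long non-serious adverse events are reported, and Section 9.4 has no period after day 30. If the 30-day sentence is applied, 60 days of scheduled follow-up have no reporting requirement for new non-serious events that are not events of clinical interest. The any-attribution serious-event window also closes 21-35 days before the 90-day visit. The resulting bias in late non-serious toxicity is downward. Its size is unknown, because the documents give no rate.

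This rests on nominal flow-chart days, on both doses being given, and on surgery falling within its scheduled range. It is a conflict with likely undercounting, not a demonstrated loss of data, and it leaves TOX monitoring untouched. Correcting it is a cheap improvement that serves the primary objective.

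**What to change.** 1. Reconcile Sections 7.6, 7.8, 8.1, 8.3.1 and 8.3.4 so that all adverse events, serious and non-serious, are reported through the later of 90 days after the last dose or the 90-day post-operative visit. Keep the existing duty to report related serious events after that.
2. Keep the last-dose anchor for patients who have no surgery or who discontinue early. They may have no 90-day post-operative visit, and Sections 5.8 and 7.14 send early discontinuers to a single visit within 30 days.
3. Align the concomitant-medication rule in Section 5.5.1, Section 7.5 and flow chart footnote 8 with the new window.
4. Add a fifth, descriptive period to Section 9.4: day 31 to day 90 after surgery.
5. Leave TOX, its 30-day post-surgical end and its stopping boundary as they are.

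The cost is extra data entry, including some concomitant medications, and the logging of some late post-operative events unrelated to the drug. No visit or test is added, and the primary analysis is not delayed.

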8.3 Reporting of Pregnancy and Lactation to the Sponsor and to Merck

Although pregnancy and lactation are not considered adverse events, it is the responsibility of investigators or their designees to report any pregnancy or lactation in a subject (spontaneously reported to them) that occurs during the trial.

Pregnancies and lactations that occur after the consent form is signed but before initiation of pembrolizumab must be reported by the investigator if they cause the subject to be excluded from the trial, or are the result of a protocol-specified intervention, including but not limited to washout or discontinuation of usual therapy, diet, placebo treatment or a procedure.

Pregnancies and lactations that occur from the time of initiation of study treatment through 120 days following cessation of study treatment, or 30 days following cessation of study treatment if the subject initiates new anticancer therapy, whichever is earlier, must be reported by the investigator. All reported pregnancies must be followed to the completion/termination of the pregnancy. Pregnancy outcomes of spontaneous abortion, missed abortion, benign hydatidiform mole, blighted ovum, fetal death, intrauterine death, miscarriage and stillbirth must be reported as serious events (Important Medical Events). If the pregnancy continues to term, the outcome (health of infant) must also be reported.

Such events must be reported within 5 working days to MDACC's IND Office and within 2 working days to Merck Global Safety. (Attn: Worldwide Product Safety; [contact])

8.4 Immediate Reporting of Adverse Events to the Sponsor and to Merck

8.3.1 Serious Adverse Events

An adverse event or suspected adverse reaction is considered "serious" if, in the view of either the investigator or the sponsor, it results in any of the following outcomes:

- Death
- A life-threatening adverse drug experience – any adverse experience that places the patient, in the view of the initial reporter, at immediate risk of death from the adverse experience as it occurred. It does not include an adverse experience that, had it occurred in a more severe form, might have caused death.
- Inpatient hospitalization or prolongation of existing hospitalization

- A persistent or significant incapacity or substantial disruption of the ability to conduct normal life functions.
- A congenital anomaly/birth defect.

Important medical events that may not result in death, be life-threatening, or require hospitalization may be considered a serious adverse drug experience when, based upon appropriate medical judgment, they may jeopardize the patient or subject and may require medical or surgical intervention to prevent one of the outcomes listed in this definition. Examples of such medical events include allergic bronchospasm requiring intensive treatment in an emergency room or at home, blood dyscrasias or convulsions that do not result in inpatient hospitalization, or the development of drug dependency or drug abuse (21 CFR 312.32).

- Important medical events as defined above, may also be considered serious adverse events. Any important medical event can and should be reported as an SAE if deemed appropriate by the Principal Investigator or the IND Sponsor, IND Office.
- All events occurring during the conduct of a protocol and meeting the definition of a SAE must be reported to the IRB in accordance with the timeframes and procedures outlined in "The University of Texas M. D. Anderson Cancer Center Institutional Review Board Policy for Investigators on Reporting Serious Unanticipated Adverse Events for Drugs and Devices". Unless stated otherwise in the protocol, all SAEs, expected or unexpected, must be reported to the IND Office, regardless of attribution (within 5 working days of knowledge of the event).
- All life-threatening or fatal events, that are unexpected, and related to the study drug, must have a written report submitted within 24 hours (next working day) of knowledge of the event to the Safety Project Manager in the IND Office.
- Unless otherwise noted, the electronic SAE application (eSAE) will be utilized for safety reporting to the IND Office and MDACC IRB.
- Serious adverse events will be captured from the time of the first protocol-specific intervention, until 90 days after cessation of study treatment, or 30 days following cessation of study treatment if the subject initiates new anticancer therapy, unless the participant withdraws consent. Serious adverse events must be followed until clinical recovery is complete and laboratory tests have returned to baseline, progression of the event has stabilized, or there has been acceptable resolution of the event.
- Additionally, any serious adverse events that occur after the time period noted above that are related to the study treatment must be reported to the IND Office. This may include the development of a secondary malignancy.

Reporting to FDA:

- Serious adverse events will be forwarded to FDA by the IND Sponsor (Safety Project Manager IND Office) according to 21 CFR 312.32.

It is the responsibility of the PI and the research team to ensure serious adverse events are reported according to the Code of Federal Regulations, Good Clinical Practices, the protocol guidelines, the sponsor's guidelines, and Institutional Review Board policy.

SAE reports and any other relevant safety information are to be forwarded to the Merck Global Safety [contact]

A copy of all 15 Day Reports and Annual Progress Reports is submitted as required by FDA, European Union (EU), Pharmaceutical and Medical Devices agency (PMDA) or other local regulators. Investigators will cross reference this submission according to local regulations to the Merck Investigational Compound Number (IND, CSA, etc.) at the time of submission.

